1.0 Objectives

1.1 Study Objectives

The overall goal of this RCT is to conduct a patient-level community-based effectiveness trial of the comprehensive, mobile app-based cognitive-behavioral intervention reSET-O, to determine whether this intervention improves the adherence to and outcome of medication assisted treatment (MAT) for opioid use disorder (OUD) in the setting of a Hub and Spoke implementation system.

This RCT is part of an R21/R33 NIH grant. The R21 pilot trial is currently underway (IRB: 00009931) with some subjective positive observations in terms of subject participation and engagement with the app. The R21 trial has laid the ground work for the R33 to be conducted successfully.

The primary hypothesis is that a greater proportion of patients assigned to Treatment As Usual (TAU) + reSET-O, compared to those assigned to TAU alone, will complete 6 months of MAT.

The Pennsylvania Psychiatric Institute (PPI) is committed to providing a wide range of high quality behavioral health services, including an Opiate Treatment Program (OTP) established in October 2017. Through the Pennsylvania Coordinated Medication Assisted Treatment (PACMAT) system, PPI functions as the "Hub," herein referred to as the PPI Hub, offering medication assisted treatment (MAT) with methadone, dispensed and prescribed buprenorphine-naloxone (suboxone) and buprenorphine (Subutex). The PPI Hub also offers extended release naltrexone to a limited number of patients. The PPI Hub also offers counseling with individual and group settings to the level of intensive outpatient treatment using evidence-based Cor-12 and Matrix model programs for groups to start. Treatment continues either at the PPI Hub or at one of the outlying spokes, depending on geography and patient clinical needs. Whether at PPI Hub or spokes, patients are assigned a case manager who meets with them regularly and coordinates their care with the prescribing physician.

The study test article, reSET-O (Pear Therapeutics, Inc.), is a commercially available version of the web-based Therapeutic Education System (TES).

1.2 Primary Study Endpoints

The primary outcome measure will be retention in treatment on MAT for 6 months after initiation.

1.3 Secondary Study Endpoints

The secondary outcome measures will be opioid use and other substance use (urine and self-report), craving, and measures of quality of life including mental health symptoms and social functioning. Exploratory analyses will examine whether the effect of reSET-O on 6-month adherence is mediated by improvements in quality of life outcomes.

2.0 Background

2.1 Scientific Background and Gaps

Medication assisted treatment (MAT) is a cornerstone of an effective national response to the epidemic of opioid use disorder (OUD). A key goal of the SAMHSA-funded State Targeted Response (STR) grants is to make MAT widely available to patients with OUD throughout the U.S. by reducing systemic barriers and increasing local capacity. However, a major barrier to the effectiveness of MAT is patient adherence. Studies show that 50% or more of patients with OUD initiating MAT will drop out of treatment within the first 3 to 6 months. Dropout is associated with a high risk of relapse and overdose, and 6 months of treatment is considered a minimum needed for most patients to enter into long term abstinence and recovery.

2.2 Previous Data

The Opioid Epidemic and Medication Assisted Treatment (MAT)

The opioid epidemic has spread rapidly over the past decade, reaching virtually every region of the U.S. It is estimated that 2.4 million Americans are currently addicted to opioids, and the prognosis is poor, if left untreated, including mortality from opioid overdose (Hser et al., 2001). Different types of MAT such as buprenorphine-naloxone, buprenorphine, methadone, and extended-release naltrexone, may be remarkably effective if patients adhere to treatment, the challenge is adherence to treatment. Studies of buprenorphine-naloxone, specifically, typically show less than 50% of patients retained in treatment for 6 months (Hser et al., 2014; Lee et al., 2017), and dropout from treatment is associated with relapse (Weiss et al., 2011; 2015; Hser et al., 2016; 2017). Hence, to combat the opioid epidemic, it is critical that MAT become universally available, and that patients' adherence to MAT be improved.

The digitally delivered intervention to be tested in this proposed study, reSET-O, targets treatment adherence, keeping appointments, and adherence to medication, while utilizing techniques of cognitive behavioral therapy and skills to avoid drug use and address problems with cravings, mood, and relationships, in order to avoid relapse, and rebuild a healthy lifestyle to support long term recovery.

Barriers to Implementation of MAT and the Penn State Hub and Spoke System

Three evidence-based Medication Assisted Treatment (MAT) approaches for treatment of opioid use disorder are approved in the U.S., methadone, buprenorphine, and extended release injection naltrexone. Maintenance treatment with methadone, a full opioid agonist, has been available for treatment of opioid use disorder since the 1970s. Methadone can only be prescribed under special regulations that are burdensome to patients (e.g. daily attendance at clinic required initially). Buprenorphine, approved in the U.S. in 2002, is a partial opioid agonist with less abuse potential, similar effectiveness, and more widespread availability than methadone, since it can be prescribed by any licensed physician who completes a modest training requirement. However, the supply of physicians actively prescribing buprenorphine remains limited. New prescribers need to be trained and supported within a variety of available clinical settings. The SAMHSA Opioid STR grants awarded to the States beginning in 2017 provided additional funding for MAT and encouraged the use of implementation models to address the shortage of prescribers, case managers, and associated services. With STR funding to the State of Pennsylvania, the Penn State-Hershey Medical Center established a Hub and Spoke (described below), based at Pennsylvania Psychiatric Institute, which is modeled on the Vermont program (Brooklyn and Sigmon 2017). This Hub and Spoke offers methadone, buprenorphine and buprenorphine-naloxone. It is within this system that the study proposed here will unfold, so that the findings may generalize to other States and regions around the U.S. utilizing similar models that support expansion of MAT through specialty clinic Hubs and primary care Spokes. All three forms of MAT are subject to substantial rates of dropout from treatment, and dropout carries a high risk of relapse to opioid use. It is our hypothesis that reSET-O will reduce dropout and hence improve the effectiveness of MAT treatment.

Barriers to Implementation of MAT: The Importance of Behavioral Therapy

Another key systemic barrier that has been identified is lack of access to behavioral intervention and counseling to accompany MAT prescribing (Quest et al., 2012; Hutchinson et al., 2014; DeFlavio et al., 2015). Provision of counseling is a regulatory requirement for methadone, buprenorphine, and buprenorphine-naloxone treatment. Further, evidence suggests that counseling and behavioral treatments improve adherence to and effectiveness of MAT (McLellan et al., 1993), particularly contingency management approaches (Peirce et al., 2006; [name] et al., 2006; Carroll and Weiss 2017). Primary care practices and other clinical settings new to treating addictions typically lack staff with expertise in relevant behavioral treatments. Even addiction treatment programs serving as "hubs" may struggle to deliver more than rudimentary counseling due to time constraints and lack of expertise in the latest evidence-based interventions. The intervention to be tested in this proposed study, reSET-O, is a comprehensive cognitive behavioral treatment, with a strong evidence-base to suggest that it can improve adherence and outcome of MAT treatment for opioid use disorder (OUD), compared to standard counseling. Since it is a mobile app, delivered through patients interacting with a smart phone, it does not require a large time commitment or behavioral health expertise of clinical staff. Thus, reSET-

O has the potential to address the need for behavioral treatment as part of STR efforts to rapidly expand MAT, while improving the effectiveness of MAT at ushering patients into stable recovery.

2.3 Study Rationale

The study proposed here would be the first randomized controlled clinical trial of a comprehensive cognitive behavioral therapy to increase the effectiveness of MAT for the treatment of OUD in the context of a regional Hub and Spoke system to expand access to MAT. Programs like the Penn State Hub and Spoke have been set up to serve rural and impoverished small urban communities that have become the epicenter of the opioid epidemic. The need to deliver evidence-based psychosocial treatment has been identified as one of the key barriers to implementing MAT in such primary care settings, where the time and expertise needed to deliver such interventions are scarce. A digitally delivered cognitive behavioral intervention such as reSET-O has the potential to fill this gap. Since reSET-O is a commercially available mobile app, if found effective in supporting MAT, it has the potential to be rapidly disseminated across the U.S. health system in support of the STR initiative.

The study of reSET-O proposed here would be the first test of a randomized control trial of comprehensive cognitive behavioral therapy (CBT) to increase the effectiveness of MAT for the treatment of OUD in the context of a regional effort to expand implementation of MAT. As a comprehensive CBT treatment, reSET-O focuses not only on drug use, craving, and medication adherence, but also on skills to help patients address common problem areas, such as relationships, mood and related problems, and social functioning, in order to rebuild a healthy lifestyle. It is also individualized in that patients can select and repeat therapy lessons relevant to their most pressing problem areas. Most evidence-based behavioral interventions are delivered by clinicians and require training and supervision of clinical staff to deliver the intervention correctly, and substantial time of clinical staff to actually deliver the intervention to patients at scale. Clinicians' time and expertise are resources that are in short supply in community-based efforts to expand implementation of MAT and have been identified as significant barriers to delivering MAT to date. If found effective in the trial proposed here, reSET-O has the potential to lead the field of MAT implementation toward a new paradigm where a behavioral intervention becomes a resource that can be down-loaded from the web and prescribed to patients, rather than an intervention that needs to be learned and painstakingly delivered by clinicians. This has the potential to promote widespread implementation of MAT both by reducing barriers to delivering behavioral therapy, and by improving adherence to MAT and overall treatment outcome. This effort may also in the long run encourage the development of other web-based behavioral interventions to support implementation of MAT.

3.0 Inclusion and Exclusion Criteria

3.1 Inclusion Criteria

- 18 years of age or older
- Diagnosis of opioid use disorder (OUD) as determined through routine clinical care
- Recently starting outpatient treatment for OUD within the PACMAT Hub and Spoke System of Care.
- Initiating MAT with buprenorphine-naloxone (suboxone), buprenorphine (Subutex), or methadone. Since buprenorphine (Subutex) is an FDA approved MAT for pregnant women with OUD, pregnant women are eligible to participate in the research study, assuming they meet all other eligibility requirements.
- Ability to read, write, and comprehend English
- Providers who are engaged with the reSET-O app and talking to their patients who have agreed to participate in the study and also assigned to use the reSET-O app.

3.2 Exclusion Criteria

- Initiating maintenance treatment that does not include MAT or switching to a maintenance treatment that does not include MAT (i.e.: detoxification and counseling treatment only without MAT).
- Planning an outpatient detoxification
- Judged by the evaluating physician or allied clinician to need a higher level of care (i.e.: residential or inpatient treatment)
- Less than 18 years of age
- Unable to read, write, and comprehend English

3.3 Early Withdrawal of Subjects

3.3.1 Criteria for removal from study

There are a number of reasons for potential subject withdrawal from the research study. If funding for the research study ends, then all subjects will be withdrawn from the research study. If it appears as though their OUD diagnosis is becoming worse, then subject will be withdrawn from the research study. This information will also be outlined in the consent form.

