3.3.2 Follow-up for withdrawn subjects

Withdrawn subjects will be categorized by why they withdrew (disease progression, etc.), and the timing of withdrawal at the 1, 3, and 6-month time points. Withdrawn subjects will not be replaced. Withdrawn subjects will have the opportunity to have a follow-up visit with the study doctor if there are any concerns regarding next steps and/or treatment.

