Participants, who do not own a smartphone, will be provided with an inexpensive tablet device that will be able to access reSET-O for the duration of the trial. These devices will be obtained and managed by research study staff. Should a participant lose or sell the tablet device, or if the device is stolen, they will be afforded a second chance with a new tablet device as provided by the study. Should the participant lose or sell the second device, or if the second device is stolen, they will not receive a third tablet device. They will still be enrolled in the study and asked to complete questionnaires at the appropriate time points; however, they may not be able to

engage with the app, reSET-O, unless they provide their own device that is compatible for use with the reSET-O app (e.g., smart phone, table). This will also be outlined in the consent form.

After obtaining consent, randomized assignment, and getting set-up with the reSET-O app (if applicable) as outlined above, all participants will complete the electronic surveys listed below.

- Eligibility checklist to assess a potential participants eligibility via inclusion and exclusion criteria.
- Demographics form will be used to collect basic demographic information on each participant (i.e.: DOB, gender, education level, etc.), and will only be collected at baseline.
- Locator form collects information that will be useful in helping research staff to locate a participant for assessment should they stop attending treatment, including address, phone number(s), and contact information of significant others who would know how to locate the participant. This is important scientifically to minimize missing data due to loss to follow up. In order to protect confidentiality of participants, if listed significant others are contacted, no information will be divulged by research staff about the participant, other than that they were participating in a survey at Penn State and the research team in attempting to contact them for follow up survey. During consent participants will be informed that it is important for research staff to be able to contact them to find out how they are doing and conduct assessments, even if they have dropped out of treatment, and the procedures for contacting significant others for locator purposes are explained.

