MAT treatment (treatment as usual) when combined with counseling has a decent success rate at greater than 50% patient retention over a 6-month period. Patients retained in MAT treatment typically experience substantial improvement in their opioid use, while those who discontinue MAT typically relapse to opioid use. Therefore it is important to try to improve the rate of retention in treatment, which is why the reSET-O intervention is proposed. Patients enrolling in the study will have been prescribed their appropriate MAT as their standard of care and is not part of the research study.

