8.3 Statistical methods

Outcome Measures and Covariates

Primary outcome: The primary outcome will be a binary indicator of whether or not the patient is retained on MAT (methadone, buprenorphine, or buprenorphine-naloxone) treatment through 24 weeks. For those who drop out before 24 weeks, time (week) of dropout will be recorded, and they will be considered as not retained.

Secondary outcomes: 1) weeks of treatment retention (time to drop-out 0-24 weeks, survival; number of weeks retained, continuous); 2) urine-confirmed abstinence from opioids in the last 4 weeks (longitudinal (weeks 4, 8, 12, and 24), binary); 3) Days using opioids in the last 4 weeks (longitudinal, continuous); 4) Days using other drugs/alcohol in last 4 weeks (longitudinal, continuous); 5) coping strategies (CSS mean score; longitudinal, continuous); 6) social functioning (EuroQol, SCS, global scores and subscales; longitudinal, continuous); 6) overall mental health symptoms (K10; longitudinal, continuous); 7) HIV risk behavior—days in past 30 of vaginal or anal sex without a condom (longitudinal, continuous); Any needle sharing in past 4 weeks (longitudinal, binary); 7) Treatment satisfaction at week 24 (IAFF; continuous); 8) Serious adverse events (binary).

Additional variables: *Covariates, primary and secondary analyses:* Stratification factors: 1) any intravenous drug use (binary); 2) treatment with methadone vs buprenorphine at Hub vs buprenorphine at Spoke (categorical). *Moderators:* 1) both stratification factors will be explored as moderators; 2) demographic characteristics (gender, age, ethnicity etc.); 3) prescription opioid use only vs any heroin or fentanyl use (binary); 4) other substance use at baseline (any cannabis, any stimulant, any heavy drinking days; binary); 5) Probable major depression at baseline (binary based on PHQ score); 6) history of prior treatment for opioid use versus first treatment episode (binary). *Mediators:* 1) social functioning (EuroQol; continuous); 2) social connectedness (SCS; continuous); 3) opioid craving (continuous); 4) coping (CSS; continuous); and 5) mental health symptoms (K10; continuous).

Intent to Treat, Dropouts, and Missing Data

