All analyses will be on the Intent-to-treat (ITT) sample, i.e., all randomized subjects (N=200) according to the treatment arm to which they were assigned. For the primary outcome, patients that dropped out before 24 weeks will be considered not retained. For the secondary outcome urine-confirmed abstinence, missing data (patients who cannot be located) will assumed to be opioid positive (not abstinent), a typical assumption which is reasonable based on the high rate of relapse among patients with OUD who discontinue medication treatment (Weiss et al., 2011; 2015; Hser et al., 2016; 2017). For other secondary outcomes, missing data will be treated as missing at random. Longitudinal mixed effects models do not require complete data to provide estimates of the outcome, and the estimates are considered valid under the assumption that the data are missing at random (Little & Rubin, 2002). We will additionally perform sensitivity analysis for the secondary outcomes to examine the influence on the outcomes of dropout and missing data by performing several imputation methods, for instance imputing missing weeks as all abstinent or all non-abstinent. Comparison of the inferences from assuming various models for the missingness provides a measure of the validity of the efficacy estimate from the initial model.

Significance Testing and Preliminary Analyses

All tests for main effects will be performed at two-sided significance level of 5%. Before performing specific analyses, we will examine the distribution of outcome measures and covariates and investigate for outliers. The distributions of continuous variables will be checked for normality, and transformed, if necessary. Distribution of demographic variables will be examined and described in terms of means, standard deviations, proportions and 95% confidence intervals. Covariates will be examined for association with treatment outcome. Covariates associated with treatment outcome will be adjusted for in models used to test study hypotheses.

Primary outcome

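### Section 3.3.1 withdraws patients from the research when OUD appears to worsen, and 3.3.2 provides for no outcome collection afterwards, so missing data can depend on how patients are doing

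*Combined protocol and SAP*

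**What the plan says.** **Withdrawal.** Section 3.3.1 states: "If it appears as though their OUD diagnosis is becoming worse, then subject will be withdrawn from the research study". The rule is mandatory and concerns the research, not just the app. The section adds that the consent form covers this too; that form was not available to check.

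**After withdrawal.** Section 3.3.2 classifies the reason, places the timing at 1, 3 or 6 months and rules out replacement. It adds that "Withdrawn subjects will have the opportunity to have a follow-up visit with the study doctor" if there are concerns about treatment or next steps. It does not mention urine, TLFB, questionnaires or MAT status.

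**Follow-up elsewhere.** Under the locator form, section 7.2.1 gives reducing missing data as a scientific aim and says that patients who leave treatment should still be contacted and assessed. For a patient who loses a second tablet it is explicit: "They will still be enrolled in the study and asked to complete questionnaires at the appropriate time points". Section 7.2.2 widens the week-24 window to allow time to find lost patients.

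**Analysis.** Section 8.3 analyses all 200 randomized patients as assigned. The primary outcome is retention on MAT through 24 weeks; for earlier dropouts, "time (week) of dropout will be recorded, and they will be considered as not retained". For urine-confirmed abstinence, "missing data (patients who cannot be located) will assumed to be opioid positive (not abstinent". Then: "For other secondary outcomes, missing data will be treated as missing at random". Sensitivity analyses under various missingness models are promised, "for instance imputing missing weeks as all abstinent or all non-abstinent".

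**The concern.** The trigger for leaving the research is closely tied to what the trial measures: opioid use, craving, mental health and, indirectly, retention. Section 10.0 recognises that opioid use may worsen in either arm, so the trigger is foreseeable. Followed as written, the rule stops observation of patients because they appear to be doing badly.

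Three things are then at stake.

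- Days of use, K10, coping and the other non-urine secondary outcomes rest on a missing-at-random model for patients selected on their condition.
- Section 8.3 does not say whether a patient withdrawn from the research while still on MAT counts as a dropout, is censored in the time-to-dropout model, or is followed through treatment records.
- The positive-if-missing urine rule can reasonably be read to cover withdrawn patients, but its wording names only those who cannot be located.

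Data that are not collected cannot be recovered at analysis.

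**Working it through.** **1. The follow-up provisions side by side.**

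| Situation | Section | Outcome collection afterwards |
|---|---|---|
| Leaves treatment | 7.2.1, locator form | Intended |
| Loses second tablet | 7.2.1 | Stated; patient stays enrolled |
| Hard to locate at week 24 | 7.2.2 | Wider window |
| Withdrawn because OUD appears worse | 3.3.1, 3.3.2 | Not provided for |

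The fourth row is the only one in which the study itself ends participation because of the patient's condition. None of the other three expressly covers it.

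**2. Outcomes treated as missing at random.** Let s be the share of an arm unobserved after withdrawal, and δ the mean amount by which the unseen values exceed the model's prediction. The error in that arm's mean is s × δ, and the error in the treatment contrast is s₁δ₁ − s₀δ₀. The documents give neither s nor δ for either arm. If the products are equal, the contrast is unaffected; if they differ, the sign can go either way. No number can be attached.

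Whether δ differs from zero depends on whether the worsening is captured before withdrawal. Visits are at baseline and weeks 4, 8, 12 and 24, so a patient can worsen and be withdrawn between visits, with up to 12 planned weeks between the last two. The one sensitivity example, all abstinent or all non-abstinent, has no direct counterpart for K10 or coping scores.

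**3. Primary outcome.** Inputs from section 8.2: 40% vs 59.7%, 100 per arm, two-sided 5%. With d the difference, SE₀ the pooled and SE₁ the unpooled standard error, power = Φ[(d − 1.96·SE₀)/SE₁].

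- Pooled rate (0.40 + 0.597)/2 = 0.4985; SE₀ = √(2 × 0.4985 × 0.5015/100) = 0.0707.
- SE₁ = √((0.40 × 0.60 + 0.597 × 0.403)/100) = 0.0693.
- Power = Φ[(0.197 − 0.1386)/0.0693] = Φ(0.84) = 80.0%, which reproduces the plan.

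The following is only an illustration. Suppose a share x of truly retained patients in both arms were withdrawn and wrongly scored as not retained. The rates become 0.40(1 − x) and 0.597(1 − x).

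| x (assumed) | Rates | Difference | Power |
|---|---|---|---|
| 0% | 40.0% vs 59.7% | 19.7 points | 80.0% |
| 2% | 39.2% vs 58.5% | 19.3 points | 78.4% |
| 5% | 38.0% vs 56.7% | 18.7 points | 75.9% |
| 10% | 36.0% vs 53.7% | 17.7 points | 71.6% |

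If the same number were misscored in each arm (5 per 100), the rates are 35.0% vs 54.7%, the difference stays at 19.7 points and power is 80.4%. If every withdrawn patient has in fact left MAT, nothing changes. Every share here is an assumption, and the conclusion does not rest on this table.

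**The case against.** The strongest reply is that the design already separates treatment from assessment. Section 7.2.1 wants treatment dropouts assessed, and section 7.2.2 allows time to find lost patients. This stands as evidence of intent and narrows the point to a conflict between sections. It does not remove it, because leaving treatment and being withdrawn from the research by the study are different events.

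Second, missingness related to outcome need not violate missing at random. If worsening shows in values recorded before withdrawal, a likelihood-based mixed model conditions on them. That is correct, so a reader who infers that the secondary analyses must be biased goes too far; the documents support only that later values could be worse than predicted. Nothing ensures that worsening is recorded first, however. Section 8.3 also refers to generalized estimating equations, which without weighting lack this protection.

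Third, section 8.3 promises sensitivity analyses for the secondary outcomes, and its example is only an illustration. This stands: the commitment exists, and what is lacking is a named analysis suited to continuous scales.

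Fourth, a reader might infer that the primary result is compromised. The documents do not support that. The outcome is retention on MAT, not in the research, and section 7.4.1 treats MAT as standard care outside the study. The same section says that "those who discontinue MAT typically relapse to opioid use", so some patients with worsening OUD may already be off MAT, and scoring them as not retained is then right.

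Finally, clinicians know who has the app, so an undefined judgement of worsening could be applied differently by arm. Nothing in the documents shows that it will be.

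**Conclusion.** The point holds in limited form. Section 3.3.1 mandates withdrawal from the research on apparent worsening, without a criterion or assessor in that section, and section 3.3.2 provides for no outcome collection afterwards. This conflicts with the intent-to-treat commitment in section 8.3 and with the follow-up aims of section 7.2.1.

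The exposure is greatest for the non-urine secondary outcomes. It is smaller for urine, where a sensible rule exists but is worded too narrowly. It is limited for the primary outcome, where what is missing is a stated source for MAT status after research withdrawal and a rule for scoring or censoring. No size or direction of bias can be derived.

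This rests on reading section 3.3 as written. If staff intend to keep following these patients, or the consent form says so, a short addition to section 3.3.2 would settle the collection question. The change should be made, with medium confidence in its practical importance.

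**What to change.** Reconcile sections 3.3.1 and 3.3.2 with 7.2.1 and 8.3:

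- **3.3.1 and 3.3.2:** separate any change in care or app use from study follow-up. State that outcome collection already scheduled (MAT status to week 24 from treatment records, TLFB, urine, questionnaires) continues for randomized patients unless consent is withdrawn.
- **8.3, retention:** state that research withdrawal alone is neither a dropout event nor a reason to censor while MAT status is known.
- **8.3, urine:** confirm that the positive-if-missing rule applies after withdrawal.
- **8.3, continuous outcomes:** name one sensitivity analysis that assumes worse values after withdrawal for worsening.

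The clinical criterion for worsening, who applies it and how such patients are managed are for the sponsor and investigator to settle.

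**Cost:** an IRB modification, revised consent wording or addenda for enrolled patients (section 5.2.1 already describes an addendum route), and some retrieval of treatment records, including from spokes. N stays at 200, and the visits and payments are already planned for all patients (sections 7.2.2 and 13.0).
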